7.2.1.3. Time period and Frequency for collecting AE and SAE information

- AEs and SAEs will be collected from the start of Study Treatment until the follow-up contact (see Section 7.2.1.5), at the timepoints specified in the Time and Events Table (Table 3 and Table 4).
- Medical occurrences that begin prior to the start of study treatment but after obtaining informed consent may be recorded on the Medical History/Current Medical Conditions section of the eCRF.
- Any SAEs assessed as related to study participation (e.g., protocol-mandated procedures, invasive tests, or change in existing therapy) or related to a GSK product will be recorded from the time a subject consents to participate in the study up to and including any follow-up contact.
- All SAEs will be recorded and reported to GSK within 24 hours, as indicated in [Appendix 3](#).
- Investigators are not obligated to actively seek AEs or SAEs in former study subjects. However, if the investigator learns of any SAE, including a death, at any time after a subject has been discharged from the study, and he/she considers the event reasonably related to the study treatment or study participation, the investigator must promptly notify GSK.

NOTE: The method of recording, evaluating and assessing causality of AEs and SAEs plus procedures for completing and transmitting SAE reports to GSK are provided in [Appendix 3](#).

7.2.1.4. Method of Detecting AEs and SAEs

Care will be taken not to introduce bias when detecting AEs and/or SAEs. Open-ended and non-leading verbal questioning of the subject is the preferred method to inquire about AE occurrence. Appropriate questions include:

- “How does your child seem to feel?”
- “Has your child had any (other) medical problems or seem to act differently in any way since his/her last visit/contact?”
- “Has your child needed to take any medicines, other than those provided in this study, since his/her last visit/contact?”

7.2.1.5. Follow-up of AEs and SAEs

After the initial AE/SAE report, the investigator is required to proactively follow each subject at subsequent visits/contacts. All SAEs and non-serious AEs of special interest will be followed until resolution, until the condition stabilizes, until the event is otherwise explained, or until the subject is lost to follow-up (as defined in Section 5.5). Further information on follow-up procedures is given in [Appendix 3](#).

7.2.1.6. Regulatory Reporting Requirements for SAEs

Prompt notification by the investigator to GSK of SAEs and non-serious AEs related to study treatment (even for non- interventional post-marketing studies) is essential so that legal obligations and ethical responsibilities towards the safety of subjects and the safety of a product under clinical investigation are met.

GSK has a legal responsibility to notify both the local regulatory authority and other regulatory agencies about the safety of a product under clinical investigation. GSK will comply with country specific regulatory requirements relating to safety reporting to the regulatory authority, Institutional Review Board (IRB)/Independent Ethics Committee (IEC) and investigators.

Investigator safety reports are prepared for suspected unexpected serious adverse reactions according to local regulatory requirements and GSK policy and are forwarded to investigators as necessary.

An investigator who receives an investigator safety report describing a SAE(s) or other specific safety information (e.g., summary or listing of SAEs) from GSK will file it with the IB and will notify the IRB/IEC, if appropriate according to local requirements.

7.2.2. Pregnancy

The investigator will collect pregnancy information on any female subject, who becomes pregnant while participating in this study. The investigator will record pregnancy information on the appropriate form and submit it to GSK within 2 weeks of learning of a subject's pregnancy. The subject will also be followed to determine the outcome of the pregnancy. Information on the status of the mother and child will be forwarded to GSK. Generally, follow-up will be no longer than 6 to 8 weeks following the estimated delivery date. Any premature termination of the pregnancy will be reported.

While pregnancy itself is not considered to be an AE or SAE, any pregnancy complication or elective termination of a pregnancy for medical reasons will be recorded as an AE or SAE.

A spontaneous abortion is always considered to be an SAE and will be reported as such. Furthermore, any SAE occurring as a result of a post-study pregnancy and is considered reasonably related to the study treatment by the investigator, will be reported to GSK as described in Section 12.3.6. While the investigator is not obligated to actively seek this information in former study participants, he or she may learn of an SAE through spontaneous reporting.

Any female subject who becomes pregnant while participating will have study treatment discontinued, but will be requested to continue study visits through the Follow-up phase.

7.2.3. Physical Exams

- A brief physical examination will include, at a minimum assessments of the lungs, cardiovascular system, and abdomen (liver and spleen).

- Investigators should pay special attention to clinical signs related to previous serious illnesses.

7.2.4. Vital Signs

Sitting pulse rate and blood pressure measurements will be performed by the investigator or qualified site staff, as outlined in Time and Events schedule ([Table 3](#) and [Table 4](#)). Measurements will be done pre-infusion/injection with the subject sitting, having rested in this position for at least 5 minutes before each reading. They will be taken before measurement of any clinic lung function tests or ECGs at the specified time point.

7.2.5. Electrocardiogram (ECG)

Twelve-lead ECGs will be performed at the visits specified in the Time and Events schedule ([Table 3](#) and [Table 4](#)).

Electrocardiogram measurements will be made after the subject has rested in the supine position for 5 minutes. The ECG should be obtained before lung function testing followed by other study procedures. Collection shortly after a meal or during sleep should be avoided since QT prolongation can occur at these times.

Investigators will be provided with ECG machines by GSK through a designated central laboratory. Paper ECG traces will be recorded at a standard paper speed of 25 mm/sec and gain of 10mm/mV, with a lead II rhythm strip. There will be electronic capture and storage of the data by a validated method, with subsequent transferral to the central laboratory for manual reading and calculation of the electrocardiographic parameters.

Subjects with evidence of significant abnormality in the 12-lead at screening will be excluded from enrolment into the Part A treatment phase.

Paper traces are required to be maintained at the site with other source documents.

7.2.6. Clinical Safety Laboratory Assessments

Clinical laboratory tests will be conducted at the visits specified in the Time and Events schedule ([Table 3](#) and [Table 4](#)). Hematology, clinical chemistry, urinalysis and additional parameters to be tested are listed below:

Table 5 Laboratory Evaluations

Hematology

Platelet Count	RBC Indices:	Automated WBC Differential:
RBC Count	MCV	Neutrophils
WBC Count (absolute)	MCH	Lymphocytes
Reticulocyte Count	MCHC	Monocytes
Hemoglobin		Eosinophils
Hematocrit		Basophils

Clinical Chemistry

BUN	Potassium	AST (SGOT)	Total and direct bilirubin
Creatinine	Chloride	ALT (SGPT)	Uric Acid
Glucose,	Total CO ₂	GGT	Albumin
Sodium	Calcium	Alkaline phosphatase	Total Protein

Routine Urinalysis

Specific gravity, pH, glucose, protein, blood and ketones by dipstick
Microscopic examination (if blood or protein is abnormal)

All blood samples which will be taken prior to each administration of study medication will be sent to a central laboratory for analysis (details provided in the Q² Solutions Investigator Manual). Standard reference ranges will be used.

Full details of the collection and shipping requirements for the central laboratory are provided in the Quest Diagnostics Clinical Trials Investigator Manual. The central laboratory will fax laboratory results to the Investigator and will transmit the results electronically to GlaxoSmithKline.

Samples will be stored securely and may be kept for up to 15 years after the last subject completes the study, or GSK may destroy the samples sooner. GSK or those working with GSK (for example, other researchers) will only use samples collected from the study for the purpose stated in this protocol and in the informed consent form. Subjects may request that their samples are destroyed at any time.

7.3. Pharmacokinetics

Blood samples for analysis of mepolizumab plasma concentration will be obtained as per the Part A Time and Events table ([Table 3](#)). Samples obtained at visit 3 and 4 must be drawn prior to mepolizumab dosing. The date and exact time of collection for each sample will be documented in the eCRF.

Details for collection and processing of samples may be found in the Q² Solutions Investigator Manual.

7.4. Pharmacodynamics

Blood eosinophil counts will be recorded as part of the standard haematological assessments performed at the visits specified in the Time and Events table ([Table 3](#) and [Table 4](#)).

7.5. Immunogenicity

Blood samples will be collected for the determination of anti-mepolizumab antibodies, prior to dosing at Visit 2 (Week 0), and subsequently at Visit 7 (Week 16), and at Visit 8 (Week 20) and Early Withdrawal.

For subjects who had a positive anti-mepolizumab antibody response at the Follow-up (Visit 8) (or last study visit at which immunogenicity was assessed if the Follow-up (Visit 8) immunogenicity sample is not available), an attempt will be made to obtain a serum sample for anti-mepolizumab antibodies at least 4 months after the last dose of study drug in Part A or upon completion of Part A, whichever is later.

In Part B, immunogenicity samples will be collected prior to dosing at Visit 15 (week 44), Visit 21 (week 68) and, when applicable, at Follow-up Visit 23 (week 80) and Early Withdrawal.

Details for sample collection and processing may be found in the Q² Solutions Investigator Manual.

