mepolizumab at Visit 2 and enter into the Treatment phase of the study. Subjects shall be observed for a minimum of 60 minutes in the clinic following each injection. Safety monitoring of subjects will occur during SC administration and for 1 hour after the three administrations in Part A and then follow monitoring policies for the center in Part B. Such monitoring will include general safety monitoring including monitoring for both systemic hypersensitivity (i.e., allergic/IgE-mediated and non-allergic) and local site reactions. In the event of an acute severe reaction (e.g., anaphylaxis) following administration of mepolizumab, there are personnel/staff onsite at the treatment facility who are appropriately trained in basic life support to manage the patient including administration of medications (e.g., epinephrine) and have access to a system that can promptly transport the patient to another facility for additional care if appropriate.

Those subjects who enter the run-in period but do not meet all inclusion/exclusion criteria will be deemed Run-in failures and will not be dosed in the study. The reason for any Run-in failure will be recorded in the eCRF.

During the Treatment phase, all subjects will receive mepolizumab either 40mg SC (subjects <40kg at Visit 2) or 100 mg SC (subjects ≥40kg at Visit 2) at week 0 (Visit 2), week 4 (Visit 3) and week 8 (Visit 4). These doses should provide therapeutic coverage through to week 12 (Visit 6/End of Therapy Visit). Visit 6 will mark the end of the treatment phase.

Subjects will visit the clinic at week 9 (Visit 5) to provide a blood sample to measure the approximate peak mepolizumab concentration.

Study visits will have a window of ± 3 days; except for Visit 5 which should be scheduled ± 1 day.

Follow-up: Following completion of Visit 6, subjects will enter into the Follow-up phase which will consist of two additional visits at weeks 16 (Visit 7) and 20 (Visit 8). For subjects who had a positive anti-mepolizumab antibody response at the Follow-up (Visit 8) (or last study visit at which immunogenicity was assessed if the Follow-up (Visit 8) immunogenicity sample is not available), an attempt will be made to obtain a serum sample for anti-mepolizumab antibodies at least 4 months after the last dose of study drug in Part A or upon completion of Part A, whichever is later.

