4.1. Overall Design

Pharmacokinetic/Pharmacodynamic Phase (Part A)

This is a multi-centre, open-label study that will assess the pharmacokinetics pharmacodynamics of three 4-weekly doses of mepolizumab, either 40 or 100mg depending on subject bodyweight, administered SC to subjects with severe eosinophilic asthma aged 6-11 years.

Long-Term Safety / Pharmacodynamic Phase (Part B)

This is a long-term safety / pharmacodynamic phase in which extended treatment for a further 52 weeks will be offered on an optional basis to those subjects eligible for continued treatment. Subjects will receive either 40 or 100mg depending on subject bodyweight, administered SC every 4 weeks to subjects with severe eosinophilic asthma

aged 6-11 years. At the end of the 52 weeks extended treatment in Part B, subjects will have an Exit Visit 4 weeks after last dose. Subjects not transitioning to the long term access program will have a Follow-Up visit 12 weeks after last dose.

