6.8. Treatment after the Completion of Part A and Part B

The investigator is responsible for ensuring that consideration has been given to the post-study care of the patient's medical condition whether or not GSK is providing specific continuing study treatment under Part B of this study.

At the end of Part A, a benefit/risk assessment will be performed by the Investigator and if this assessment supports continued therapy with mepolizumab the subject will be offered the opportunity to enrol in Part B following the Part A Follow-up visit (Visit 8). Part B will continue for 52 weeks of additional mepolizumab treatment.

At the end of Part B, when feasible, subjects will transition to a long term access program. At the end of the Treatment Phase of Part B, subjects that are not able to transition to the long term access program will return to usual care and will be prescribed appropriate alternative asthma therapy, as required.

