 2. For subjects who had a positive anti-mepolizumab antibody response at the 12 week post-last-dose follow-up assessment (Visit 8) (or last study visit at which immunogenicity was assessed if the Follow-up (Visit 8) immunogenicity sample is not available) an attempt will be made to obtain a serum sample for anti-mepolizumab antibodies at least 4 months after the last dose of study drug in Part A or upon completion of Part A, whichever is later.
 3. Exit visit should be performed as close as possible to the planned week 12 visit date.
 4. Therapy history to include a detailed review of prior biologics received for treatment of asthma, including prior investigational anti-IL5 or anti-IL13 preparations.
 5. During the treatment period, all lab samples and procedures should be obtained prior to study treatment administration.
 6. A positive Hepatitis B Surface Antigen and Hepatitis C antibody is exclusionary
 7. This immunogenicity sample must always be collected 12 weeks (\pm 7 days) post-last-dose of study treatment; therefore, for subjects who withdraw from study treatment early, this sample must be collected 12 weeks (\pm 7 days) after their confirmed last dose of study treatment (i.e., prior to Visit 8). In the event that this sample collection date coincides with an Early Withdrawal Visit, only one immunogenicity sample should be collected.
 8. Visit 8 to be performed 12 weeks post last dose. For subjects continuing into the long-term extension phase Part B, Visit 9 should be conducted on the same day as Visit 8 once all of the visit 8 assessments have been completed. Assessments performed at Visit 8 that are also listed for Visit 9 should not be duplicated if Visit 8 and Visit 9 are performed on the same day.

Table 4 Time and Events Table Long-Term Safety / Pharmacodynamic Phase (Part B)

Procedure	Eligibility Check / First Dose	Treatment Period													Exit Visit	Follow-up ³	Early Withdrawal
Visit	9	10	11	12	13	14	15	16	17	18	19	20	21	22	23		
Week of Study (visit window \pm 5 days)	20	24	28	32	36	40	44	48	52	56	60	64	68	72	80		
Subject Screen																	
Informed consent	X ¹																
Inclusion and exclusion criteria	X ¹																
Safety Assessments																	
Concomitant medications	X	X	X	X	X	X	X	X	X	X	X	X	X	X	X	X	
Hematology (including eosinophils) ²	X			X			X			X			X	X	X	X	
Clinical Chemistry ²	X			X			X			X			X	X		X	
12-lead ECG														X		X	
Vital signs	X	X	X	X	X	X	X	X	X	X	X	X	X	X	X	X	

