Bodyweight	X	X ¹	X ¹	X ¹	X ¹	X ¹	X ¹	X ¹	X ¹	X ¹	X ¹	X ¹	X ¹				
Adverse events	X	X	X	X	X	X	X	X	X	X	X	X	X	X	X	X	
Cardiovascular events	X	X	X	X	X	X	X	X	X	X	X	X	X	X	X	X	
Liver events	X	X	X	X	X	X	X	X	X	X	X	X	X	X	X	X	
Laboratory Assessments²																	
Urinalysis	X ¹					X								X		X	
Pregnancy Test	U	U	U	U	U	U	U	U	U	U	U	U	U	U	U	U	
Blood sample for immunogenicity ²							X						X		X	X	
Outcomes Assessments																	
FEV1	X ¹			X			X			X			X	X	X	X	
ACQ-7	X ¹			X			X			X			X	X	X	X	
C-ACT	X ¹			X			X			X			X	X	X	X	

Procedure	Eligibility Check / First Dose	Treatment Period												Exit Visit	Follow-up ³	Early Withdrawal
Visit	9	10	11	12	13	14	15	16	17	18	19	20	21	22	23	
Week of Study (visit window \pm 5 days)	20	24	28	32	36	40	44	48	52	56	60	64	68	72	80	
Assessment of exacerbation	X	X	X	X	X	X	X	X	X	X	X	X	X	X	X	X
Investigational Product																
Mepolizumab SC dose administered	X	X	X	X	X	X	X	X	X	X	X	X	X			
Study Administration																
Email to GSK Operational Lead	X	X	X	X	X	X	X	X	X	X	X	X	X	X	X	X
Complete eCRF	X	X	X	X	X	X	X	X	X	X	X	X	X	X	X	X

1. Bodyweight will be measured at Visit 9 and at each visit until such time as the subject reaches 40kg in weight. Subjects with bodyweight \geq 40Kg at Visit 9 will not be weighed again during Part B.
2. All laboratory samples should be collected prior to the administration of study medication
3. The 12-week post-dose follow-up visit (Visit 23) is not required for subjects transitioning to the long-term access program.

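### Children moving to the access programme have no antibody sample after the last Part B dose, and the SAP pools them with children sampled at Week 80

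*Protocol*

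**What the plan says.** The frequency of binding and neutralising antibodies is among the Part B primary endpoints, under an objective that covers 52 weeks (Protocol Section 3). Section 7.5 sets the Part B timing: blood "will be collected prior to dosing at Visit 15 (week 44), Visit 21 (week 68) and, when applicable, at Follow-up Visit 23", which falls at Week 80, with a further sample at Early Withdrawal. Table 4 agrees: the row "Blood sample for immunogenicity" is marked at Visits 15, 21 and 23 and at Early Withdrawal, and not at Visit 22. Haematology and clinical chemistry are both marked at Visit 22.

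Table 4, footnote 3: "The 12-week post-dose follow-up visit (Visit 23) is not required for subjects transitioning to the long-term access program". Section 6.8 makes that transition the default: "At the end of Part B, when feasible, subjects will transition to a long term access program". Section 4.1 fixes the exit visit: "subjects will have an Exit Visit 4 weeks after last dose".

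SAP Section 8.2.2.1 tabulates ADA results by treatment group and visit and, in the same table, each child's highest post-baseline result. A similar table is planned for NAb. SAP Tables 3.63 and 3.64 break Part B adverse events down by highest ADA result. The SAP is based on Amendment 4, and its design summary still gives every Part B subject a visit 12 weeks after the last dose.

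**The concern.** The endpoint is meant to describe antibody formation over the whole 52-week extension. A child who transitions completes Part B, so the Early Withdrawal sample does not apply, and the final dose is never followed by an antibody sample. Because transition is the default where feasible, this may apply to most completers.

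The second issue is the summary. A highest-ever result depends on how many samples a child has and when they were taken. Children who attend Visit 23 have one more sample, at 12 weeks off drug. Combining the two groups in one frequency, and then classifying adverse events by it, mixes unequal chances of detection. The SAP does not address this because it predates the waiver.

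**Working it through.** **Inputs.** Part A doses at Weeks 0, 4 and 8 (Protocol Section 4). First Part B dose at Visit 9, on the same day as Visit 8, Week 20 (Table 3, footnote 8). Then 4-weekly doses from Week 24, the last marked at Visit 21, Week 68 (Table 4). Part B ADA samples at Weeks 44 and 68 pre-dose, and at Week 80 where applicable (Section 7.5).

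**Reproducing the plan's schedule.**
- Last Part A dose + 12 weeks: 8 + 12 = Week 20 (Visit 8).
- Number of Part B doses: (68 − 20)/4 + 1 = 13.
- Exit visit: 68 + 4 = Week 72. Follow-up visit: 68 + 12 = Week 80.
- Part B duration: 80 − 20 = 60 weeks, or 72 − 20 = 52 weeks for transitioning children. Both match Sections 4 and 4.2.

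**Coverage for a transitioning child.**
- Part B doses given before the Week 44 sample: Weeks 20 to 40, (40 − 20)/4 + 1 = 6.
- Part B doses given before the Week 68 pre-dose sample: Weeks 20 to 64, (64 − 20)/4 + 1 = 12 of 13.
- Time covered: 68 − 20 = 48 of 52 weeks. Unobserved: 52 − 48 = 4 weeks, or 4/52 = 7.7%.

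**Scheduled Part B samples per completing child.**

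| | Weeks sampled | Number | Doses followed by a sample |
|---|---|---|---|
| Attends Visit 23 | 44, 68, 80 | 3 | 13 of 13 |
| Transitions, as planned | 44, 68 | 2 | 12 of 13 |
| Transitions, with a Visit 22 aliquot | 44, 68, 72 | 3 | 13 of 13 |

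The Visit 22 aliquot equalises the number of samples and covers every dose. It does not equalise timing: 72 − 68 = 4 weeks after the last dose, against 80 − 68 = 12 weeks.

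**The Part A re-sample.** A child who is ADA-positive at Visit 8 (or at the last assessed visit) is to be re-sampled, if possible, "at least 4 months after the last dose of study drug in Part A or upon completion of Part A, whichever is later". Four calendar months are 120 to 123 days, and Week 8 is day 56, so the earliest date is (56 + 120)/7 = Week 25.1 to (56 + 123)/7 = Week 25.6. That is later than Week 20, so the 4-month limb governs. A child in Part B has by then been dosed at Weeks 20 and 24. Across all combinations of the ±3-day and ±5-day visit windows, 23,639 of 23,716 (99.7%) give two prior Part B doses and 77 (0.3%) give one. If 4 months is read as 16 weeks, the earliest date is 8 + 16 = Week 24, after one dose if the sample is taken pre-dose.

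**The case against.** The strongest reply is that little is lost. Transitioning children are sampled at Week 44 and at Week 68, 48 weeks into a 52-week phase. As planned they have no off-drug period to follow, and the waiver was a deliberate Amendment 5 change. The Part A off-drug sample is intact, because Visit 9 dosing comes only after the Visit 8 assessments. The by-visit table already gives Week 80 its own row, so only the highest post-baseline row pools. The analysis is descriptive, with no hypothesis test. All of this stands, and it limits the point to one uncovered dose and one pooled summary.

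A reader might infer that antibody follow-up fails for children who stay on drug. The documents do not support that, given the Week 44 and Week 68 samples. The Part A rule ("This immunogenicity sample must always be collected 12 weeks" after the last dose) does not contradict the Part B schedule either; it belongs to the Part A table and shows only what Part A required.

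A reader might also infer that the 4-month re-sample is worthless for Part B entrants and should be limited to children who stop. That does not follow. No section says its only purpose is to show persistence off drug. Without it, an ADA-positive child re-exposed at Week 20 could go unsampled until Week 44, a gap of 24 weeks. Nor is an extra needle established: the timing has no upper limit, so the sample could be taken with the scheduled Week 32 draw. Masking of antibody by circulating drug cannot be claimed, because the documents give no drug-tolerance limit for the assay.

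**Conclusion.** The point holds as a modest improvement. For children who transition, the last scheduled ADA sample follows 12 of 13 Part B doses, and the last 4 of 52 weeks of a primary endpoint are unobserved. The SAP's highest post-baseline ADA and NAb summaries, and the adverse event tables built on the ADA result, combine these children with others who have a further sample 12 weeks after the last dose.

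This rests on the current Section 7.5 and Table 4, which agree with each other, and on nominal visit weeks. The documents do not say how many children will transition, so the effect on the reported frequency cannot be estimated; it could range from none to all Part B completers.

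On the re-sample, a note on interpretation is enough. For a Part B entrant, a result at about Week 25 or later follows one or two Part B doses at the earliest permitted date, and more if the sample is taken later. It should be read as an on-treatment result, not as evidence of persistence off drug. This concerns only ADA-positive children who enter Part B, and the protocol promises only an attempt at the sample.

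**What to change.** 1. In Protocol Section 7.5 and Table 4, add an ADA aliquot to the existing Visit 22 (Week 72) blood draw for children who will not attend Visit 23.
2. In the SAP, update the Part B schedule for the Visit 23 waiver. Report the highest post-baseline ADA and NAb summaries separately for children with and without a Week 80 sample. Keep the by-visit tables as planned.
3. In the SAP, state that a Part A re-sample taken after Part B dosing has begun is an on-treatment result. Leave the re-sample rule itself unchanged.

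The cost is amendment wording plus one extra aliquot and one assay per transitioning child, with no additional venepuncture. The reporting split needs no new data, but it divides an already small group. The limitation remains that a sample 4 weeks after the last dose does not replace one at 12 weeks, so the split is still needed once the aliquot is added.
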